5.2 Study Outcome Measures

5.2.1 Primary Outcome Measure

The primary outcome is clinically diagnosed diarrhea anytime within 14 days of enrollment. Diarrhea is clinically defined as three or more loose stools per day for two consecutive days. This will be a dichotomous (yes or no) outcome of diarrhea during the 14-day period.

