11.4.2 Microbiome Community Profiling

16S rRNA gene amplification, sequencing and raw 16S rRNA data processing: The gut microbiota will be characterized by sequencing bacterial 16S rRNA gene amplicons from stool samples. A region of ~469 bp encompassing the 16S V3-V4 hypervariable regions[110-113] will

be targeted for sequencing using MiSeq's 300 bp paired-end sequencing reads and the two universal PCR primers 319F and 806R,[114] according to procedures previously published at The Institute for Genome Sciences (IGS) at the University of Maryland School of Medicine.[115, 116] Barcoding[114] will be used to multiplex >400 samples per MiSeq run, which will provide a sampling depth (~20,000 read pairs) sufficient to characterize the microbiota with high resolution. Raw 16S rRNA reads will be processed using published protocols.[114, 117, 118] Within- (alpha-diversity) and between- (beta-diversity) sample comparisons will then be performed using QIIME.[119] Enterotype classification will be carried out using the methods of Arumugan[120], as modified by the [name] laboratory.

Microbiota will be compared cross-sectionally and longitudinally, using parameters such as diversity and evenness (Shannon, Simpson index), and similarity (phylogenetic UniFrac distance, Jensen-Shannon divergence), determined using standard tools, such as Mothur,[121] QIIME,[119] and statistical R package (www.r-project.org). In addition, statistically significant correlations between specific microbiota members and post-BB-12 time points, subject clusters, and clinical outcomes will be determined using bioinformatics tools, such as eLSA,[122] Metastats,[123] and LEfSe.[124] Since there is no universal standard for such correlations, we will use all existing statistical tools developed to analyze 16S rRNA gene datasets. We will incorporate in our analysis any new statistical tool developed during the course of the study by either IGS researchers or external laboratories. The 16S dataset will also be used to simulate microbiota functional compositions using PiCRUSt,[125] which uses available genome sequence data to infer functional gene contents based on the 16S rRNA microbiota compositions. This method will provide an alternative access to functional microbiota characterizations.

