11.4.3 Anticipated Results and Interpretation

The experiments described in this aim will provide us with sequential samples from which data on both microbial composition (based of 16S rRNA profiling) and community function (based on RNASeq data) can be generated. We anticipate that longitudinal 16S rRNA profiling will provide insight into a number of distinct shifts in the microbiota (i.e., loss of particular taxa, loss of overall community diversity) that reflect the impact of antibiotics (control group) and antibiotics plus BB-12 (active yogurt group).

The impact of antibiotic treatment on the microbiota: In this clinical trial, all participants will be treated with a 7-10-day course of antibiotics beginning on day 1, and will be followed for another 20-23 days following cessation of antibiotic therapy. We will assess changes in the microbiota at five time points over this 30-day period. This study design will provide us an opportunity to capture information on antibiotic-induced changes in the microbiota, as well as monitor the recovery of the microbiota in 300 participants. We anticipate that a subset of participants will develop diarrhea, and we will generate data on microbiota changes during the progression from the diarrheal state to the non-diarrheal state. This will allow us to ask if changes in the relative abundance of specific members of the gut microbiota (either alone or in combination) correlate with clinical outcome. To our knowledge, there have been no studies that examine the microbiota during the progression to a diarrheal state and the resolution of the diarrheal state. There have been limited studies on the treatment with antibiotics,[47, 126] but not in the context of disease resolution, nor in a pediatric population. We anticipate these findings will be novel and provide insight into the dynamics of the human gastrointestinal tract.

We will also use the baseline16S rRNA data to identify gut enterotypes in the 300 participants in this clinical trial. With regard to this aspect of data analysis, we will test the hypothesis that specific enterotypes are more/less resistant to development of antibiotic-induced diarrhea and more/less likely to show complete recovery of community structure following antibiotic

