13.1 Data Management Responsibilities

Data Coordination will be provided by the biostatistician and the CAPRICORN research network.

The following data collection forms will be double-entered into the database:

Adverse Event Report Form (AE)

Baseline Health Status (BH)

Daily Assessment Diary (DD)

Demographic Information Form (DI)

Follow-up Form (FU)

Inclusion/Exclusion Form (IE)

Randomization Form (RZ)

Serious Adverse Event Report Form (SA)

The following data collection forms will be single-entered into the database:

Day 180 Follow-up Form (OF)

Diarrhea Report Form (DR)

Diarrhea Follow-up Form (DF)

Diet Recall Diary (DT)

Informed Consent Process Documentation (IP)

Missed Contact Report Form (MC)

PedsQL (Pediatric Quality of Life Inventory) (PQ)

Sample Collection Form (SC)

Withdrawal from Intervention Form (WI)

Yogurt Consumption Follow Up (YC)

All of these forms will be used as source documents for the study. There are 18 data collection forms in total.

Each form has a two character abbreviation that will be used throughout the study to identify the forms. The data system uses this abbreviation to identify the form. The abbreviation, plus a revision number, must be entered into the system to identify every form prior to entry. The revision number refers to changes in forms that may occur after the study starts. At the start of the study, all forms have revision number 1, i.e. the Adverse Event form is referred to as AE1.

The databases will be created using REDCap [130]. All data and forms entered will be automatically validated upon entry into REDCap (range, type, and branching logic). Using the Double Data Entry Module, the data entry system is designed for independent double data entry—where the eight specified forms would be entered twice by two different RAs. This method of data entry helps to ensure data quality and accuracy. The data coordinator will provide two separate entry records and therefore two separate databases per Study ID:

Database 1 will be considered the primary database and Database 2 will be considered the secondary database. Each RA will be given access to only 1 entry record per Study ID. Each

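### Aim 3 relates post-baseline stools to diarrhea without ordering them by onset, so those associations cannot be told apart from consequences of the diarrhea

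*Combined protocol and SAP*

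**What the plan says.** All references are to the combined protocol and SAP.

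- **Outcome (5.2.1).** The outcome is "clinically diagnosed diarrhea anytime within 14 days of enrollment", scored yes or no. An episode is three or more loose stools a day on two consecutive days.
- **Stool schedule (9.2, 9.3, Table 8).** One stool before the first yogurt, then Days 7, 14, 21 and 30, each ±2 days. No sample is tied to onset.
- **Taxon analysis (11.4.2).** "Microbiota will be compared cross-sectionally and longitudinally", and "statistically significant correlations between specific microbiota members and post-BB-12 time points, subject clusters, and clinical outcomes will be determined" with general tools such as eLSA, Metastats and LEfSe.
- **Purpose (11.4.3).** The plan will "ask if changes in the relative abundance of specific members of the gut microbiota (either alone or in combination) correlate with clinical outcome". The sentence before this says "we will generate data on microbiota changes during the progression from the diarrheal state to the non-diarrheal state". The sentence after it says that no known studies "examine the microbiota during the progression to a diarrheal state and the resolution of the diarrheal state".
- **Enterotypes (11.4.3).** The hypothesis on resistance to developing diarrhea uses baseline 16S data only.
- **Expression (11.4.4, 11.4.5).** RNA comes from baseline and Day 7 stools. The budget is 100 samples, for about 50 children expected to have diarrhea. Section 11.4.5 then discusses profiles in subjects who do or do not develop AAD.

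**The concern.** Two questions need different stools. What precedes diarrhea can be answered only from stools collected before onset. What diarrhea does to the microbiota, and how it recovers, needs stools from onset on. Section 11.4.3 lays claim to both, but the plan has no rule that assigns a stool to one or the other.

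A case's Day 7 stool may come before or after the episode, and Day 14, 21 and 30 stools almost always come after it. If cases and non-cases are compared at these visits, a taxon that changed only because the child had diarrhea, or because of how it was managed, shows an association with clinical outcome. The association is real, but its direction is unknown. At stake is whether Aim 3 can say anything about progression to diarrhea beyond the baseline sample.

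**Working it through.** **1. Inputs from the plan.** Section 11.2 gives AAD rates of 22% (control) and 8% (BB-12) with 150 per group. These reproduce the stated power of 0.92: the null SE is √(2×0.15×0.85/150) = 0.0412 and the alternative SE is √((0.22×0.78 + 0.08×0.92)/150) = 0.0404. Then (0.14 − 1.96×0.0412)/0.0404 = 1.46, which gives power 0.93.

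Expected cases are 150×0.22 + 150×0.08 = 33 + 12 = **45**, leaving 255 non-cases. Section 11.4.4 works with about 50, which is the same order.

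**2. What the design fixes.** Section 7.3 excludes active diarrhea, so the baseline stool precedes onset. An episode needs two consecutive days within 14, so its first day is Day 13 at the latest. A stool taken on Day 14 or later therefore follows onset in every case. One taken on Day 12, the early edge of the window, would precede only a Day 13 onset.

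**3. What must be assumed.** The documents give no distribution of onset day. Share of cases whose Day 7 stool is on or after onset:

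| Assumed first day of episode | Day 7 | Mean of Days 7, 14, 21, 30 |
|---|---|---|
| Uniform, Days 1-13 | 7/13 = 54% | (0.54+3)/4 = 88% |
| Uniform, Days 2-13 | 6/12 = 50% | (0.50+3)/4 = 87.5% |
| All on Days 2-7 | 100% | 100% |
| All on Days 8-13 | 0% | 75% |

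Under uniform onset over Days 1-13, moving the Day 7 stool across its ±2-day window gives 5/13 to 9/13, or 38% to 69%. Onset timing matters far more than the visit window.

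**4. Consequence for a test.** Illustrative simulation: 45 cases and 255 non-cases; a taxon with no difference before onset and a shift of *s* SD from onset on, still present at Day 14; an unadjusted Mann-Whitney test at 0.05. The plan does not name this test, and *s* and its persistence are assumptions. Share of runs in which the taxon is flagged (10,000 runs per cell):

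| Onset | *s* | Day 7 | Day 14 |
|---|---|---|---|
| Uniform, Days 1-13 | 0.5 | 36% | 85% |
| Uniform, Days 2-13 | 0.25 | 11% | 32% |
| Uniform, Days 2-13 | 0.5 | 32% | 85% |
| Uniform, Days 2-13 | 1.0 | 80% | 100% |
| All Days 2-7 | 0.5 | 85% | 85% |
| All Days 8-13 | 0.5 | 5% | 85% |

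**5. With an onset rule.** Keeping only cases still free of diarrhea at the Day 7 stool returns the rate to about 5% under both uniform scenarios. A baseline-only comparison is at about 5% in every scenario.

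**The case against.** The strongest reply is that the plan promises only correlation with clinical outcome, in a sentence introduced by the move out of the diarrheal state. For that purpose post-onset stools are the intended data, and flagging a taxon that diarrhea changed is not an error. The one explicit hypothesis about developing diarrhea, on enterotypes, is already restricted to baseline. The plan also foresees longitudinal comparison, and an analyst could date stools against onset without any change to collection. All of this stands, and it limits the point.

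A reader might infer more than the documents support:

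- *That taxa altered by diarrhea will be reported as leading to it.* The plan does not say so. What follows is that its post-baseline analyses could not tell the two apart.
- *That all of Aim 3 is affected.* It is not. The baseline enterotype analysis is correctly ordered, and the comparison of microbiota between yogurt groups does not condition on diarrhea.
- *That each child is coded as a case at every stool.* Section 11.4.2 does not say how outcome is coded.
- *That these correlations are offered as showing who responds to BB-12.* That language is in 11.4.5 and concerns enterotypes.
- *That the flagging rates are properties of the trial.* They depend on an assumed onset pattern and shift. If every onset falls on Days 8-13, an on-schedule Day 7 stool has no such problem.

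What the reply does not meet is the reference to progression toward diarrhea in 11.4.3, or the reading of Day 7 expression by whether AAD develops in 11.4.5. Both need ordering by onset. Longitudinal comparison and named software do not supply it.

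**Conclusion.** The gap is real but limited. Post-baseline taxon-diarrhea correlations (11.4.2, 11.4.3) and the Day 7 expression contrast (11.4.4, 11.4.5) mix stools from before and after onset. They cannot be distinguished from consequences of diarrhea and cannot support statements about progression to it.

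For Days 14 to 30 the mixing of purpose follows almost entirely from the 14-day outcome window. For Day 7 it could be absent or complete (0-100%), and is about half if onset is uniform. For an assumed 0.5 SD shift, the flagging rate runs from about 5% to 85% at Day 7 and is about 85% at Day 14 if the shift persists.

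This is an exploratory part of a secondary objective. The primary Fisher test, the safety analysis and the baseline enterotype analysis are untouched.

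**What to change.** In 11.4.2 to 11.4.5:

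1. Define onset as the first day of an episode that meets the 5.2.1 definition, dated from the Day 1-14 diary and the Diarrhea Report Form. An isolated loose stool is not onset.
2. Label each stool pre-onset or on/after onset, using the collection date on the stool label (9.5) and the Sample Collection Form (13.1).
3. Limit analyses of developing diarrhea to baseline stools, and to Day 7 stools from children still free of diarrhea at that stool. Compare later cases with children who stay diarrhea-free, adjusting for treatment arm, which the plan expects to affect both diarrhea and microbiota.
4. Analyse on/after-onset stools separately and describe the results as consequence or resolution.
5. Apply the same labels to the Day 7 RNA samples. The 100-sample budget is set aside for children with diarrhea, so state where the expression data for diarrhea-free children will come from, or confine the analysis to within-case comparisons.

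I would not adjust for the Bristol score on the collection day. The diary ends at Day 14, so later stools have no score, and before onset stool form may be part of the process being studied.

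**Cost.** A few sentences and one derived variable, with no new clinical data collection. Early-onset cases leave the Day 7 predictive contrast: with uniform onset over Days 2-13, about 22 of 45 remain (0 if all onsets are on Days 2-7, 45 if all are on Days 8-13). By the normal approximation, the difference detectable with 80% power at 0.05 rises from 2.80×√(1/45+1/255) = 0.45 SD to 2.80×√(1/22+1/255) = 0.62 SD. The excluded cases still contribute at baseline and in the post-onset analysis.

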11.4.4 Metatranscriptomics

16S rRNA amplicon sequencing will provide an inventory of community members in the gut microbiota, whereas metatranscriptomics will provide an actual snapshot of the expressed genes -- moving the studies from descriptive to mechanistic. RNA will be isolated from the baseline and day 7 samples (funding limitations preclude metatranscriptome analysis of all samples; however, frozen samples will be available for future gene expression profiling studies if deemed to be of interest). We have budgeted for 100 samples to be analyzed, as we anticipate about 50 participants will have diarrhea, and the gene expression profiles of the microbiota at baseline and day 7 samples from these individuals will be analyzed.

Isolation of total RNA, host and bacterial rRNA depletion, mRNA amplification, library preparation and metatranscriptomic sequencing: Total RNA will be extracted from stools using an acid-phenol protocol, as described in Eloe-Fadrosh et al.[109] rRNA removal will be accomplished using the RiboZero Bacterial and Human rRNA Removal Kits, which consistently remove ~99% of all rRNA as estimated by the percent of RNAseq reads matching to any rRNA gene (SSU and LSU). The purified and rRNA-reduced RNA will be used to create indexed sequencing libraries to be multiplexed for sequencing. Analyses of the metatranscriptomic data will include mapping to reference genomes. We will use Bowtie to map sequence reads to our growing database of reference genome sequences that currently includes 1,482 and 1,941 non-redundant isolates.

Annotation and metabolic reconstructions: Reads that map to reference genomes will be converted into contigs on which the reference genome annotations will be transferred, and subsequently used for metabolic reconstruction using the Pathway Tools package developed by [name] for the semi-automated prediction of metabolic pathways and full pathways visualization via web browser. In addition, HUMAnN2 (HMP Unified Metabolic Analysis Network)[128] will be used for accurate determination of presence/absence of microbial pathways, in the form of abundance tables summarizing gene families and metabolic pathways present in a given microbial community. This facilitates the analysis of a collection of metatranscriptomes as a matrix of gene/pathway abundances, similar to a collection of microarrays. Differential gene expression analysis will be carried out, as described in Eloe-Fadrosh et al.[109]

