5.1.2 Secondary Objectives

Objective 2: To assess the safety of yogurt supplemented with BB-12.

Objective 3: To carry out longitudinal community structure and gene expression analysis of fecal microbiota to evaluate the impact of high dose BB-12 in a pediatric population receiving antibiotics.

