11.2 SAMPLE SIZE CONSIDERATIONS

Sample Size Calculation for the Primary Outcome: This study is a double blinded, randomized Phase II trial where subjects will be randomly assigned (1:1) to either a probiotic (BB-12) yogurt group or to a control yogurt group. The primary outcome is dichotomous, clinically diagnosed diarrhea or no diarrhea, with the rate of AAD in the general population estimated to be 20-35%. Preliminary results from the Cochrane review showed the incidence of AAD in a high dose probiotic group to be 8% versus 22% in a control group.[108] Using the Cochrane estimates, a total sample of 300 subject (150 per group) would provide a power of 0.92 for detecting a difference of 0.14 (0.22 control - 0.08 probiotic) at alpha = 0.05, 2-tailed. To allow for one interim analysis (at approximately 50% recruitment), and then adjusting the final p-value to 0.029, the power would still be 90% for detecting the difference of 0.14 in the rates of AAD. If the difference in the final rates is smaller than 0.14, such as 0.12, the resulting power would still be sufficiently large (80%) and power would be equal to 74% if the final difference in rates were equal to 0.10. While the hypothesis is one-sided (see Aim 1; we expect children receiving probiotic intervention will demonstrate less AAD than those receiving the control product), we still used a two-tailed alternative for estimating the sample size in order to be conservative. While multiple efforts are arranged to minimize loss of data, in order to obtain the primary outcome (diarrhea or no diarrhea), there still will be some participants lost to follow-up and the endpoint is unknown. Nonetheless, if the lost to follow-up rate is as high as 10% (then N=270, approximately 135 per group), power would still be 90% for detecting the difference of 0.14 and 80% for detecting a difference of 0.12.

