11.4.5 Anticipated Results and Interpretation

Gene expression and pathway reconstruction for the community: The metatranscriptomic studies will provide information about the gene expression profiles of all members of the microbiota as well as the *in vivo* expression profile for the probiotic, BB-12. Together, these data

will provide insight into (i) which organisms are metabolically active in the presence of antibiotic with and without BB-12; and (ii), whether the gene expression profile of BB-12 is similar in all patients. We anticipate that we will identify different transcriptional profiles that are associated with (i) administration of antibiotic alone or (ii) the concomitant administration of antibiotics and yogurt in subjects that either develop AAD or do not. What is not known is whether these transcriptional programs will differ depending on clinical outcome and/or the starting composition of the microbiota and/or the ingestion of BB-12. It is possible that each gut enterotype will exhibit a differential response to BB-12, in terms of changes in community composition, and/or gene expression. Such a finding will be of value in understanding the parameters that identify those subjects most likely to respond to probiotic intervention.

Antibiotic resistance gene expression profiles: With the increase in prevalence of antimicrobial resistance among bacterial pathogens and in environmental samples, investigators at IGS have developed bioinformatics pipelines for the identification of resistance genes in metagenomic/metatranscriptomic samples. The current iteration of the analysis pipeline identifies a total of 121 reference markers (representing 357 allelic variants) in the proposed reference database, based either on the screening of previously published literature or based on our own ongoing work in this field. Therefore, we have the ability to identify antibiotic-induced increases in resistance gene expression in the metatranscriptomics dataset and we will include this information as part of the analysis. Collectively, the work to be carried out as part of Aim 3 will provide the most robust description of metatranscriptome changes in association with concomitant antibiotic and probiotic administration to date.

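### Gene-expression sequencing is assigned only to children with diarrhea, so the planned AAD versus non-AAD expression comparison has no comparison group and any BB-12 versus control expression contrast is not randomized

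*Combined protocol and SAP*

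**What the plan says.** Objective 3 (section 5.1.2) includes "gene expression analysis of fecal microbiota to evaluate the impact of high dose BB-12 in a pediatric population receiving antibiotics". Section 11.4.4 explains that "funding limitations preclude metatranscriptome analysis of all samples; however, frozen samples will be available for future gene expression profiling studies". It then fixes the scope: "We have budgeted for 100 samples to be analyzed, as we anticipate about 50 participants will have diarrhea". Which material is sequenced is settled in the second half of that sentence: "the gene expression profiles of the microbiota at baseline and day 7 samples from these individuals will be analyzed". Footnote 2 of Table 8, attached to the metatranscriptome row, gives the same rule: the analysis covers every participant who meets the clinical definition of diarrhea. No other group is named anywhere.

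Section 11.4.5 describes what the expression data are expected to show:

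- "which organisms are metabolically active in the presence of antibiotic with and without BB-12";
- "whether the gene expression profile of BB-12 is similar in all patients";
- profiles associated with antibiotic alone or with "the concomitant administration of antibiotics and yogurt in subjects that either develop AAD or do not".

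It also asks whether expression differs by clinical outcome and by BB-12 intake. Section 11.4.6 then looks for correlations between clinical outcomes, 16S and expression data.

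**The concern.** The sampling rule and the stated questions do not match, in three ways.

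1. **AAD versus non-AAD.** A comparison by outcome needs children from both sides. The rule supplies only cases.
2. **BB-12 versus control.** Diarrhea within 14 days of enrollment is the primary outcome, so it arises after randomization and BB-12 is expected to reduce it. Comparing arms among cases conditions on that outcome. If BB-12 works, the BB-12 cases are those who had diarrhea despite it, while the control cases include children whom BB-12 would have protected. Randomization does not make these groups comparable. Likewise, BB-12's own expression would be read only from BB-12 children who had diarrhea, not from all patients.
3. **Open-ended rule.** Table 8 takes every child with diarrhea, but the budget covers 50 children and nothing says which are taken if there are more.

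Once the libraries are spent on cases, the budget for a comparison group is gone.

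**Working it through.** **Inputs.** 100 libraries, two per child (baseline and Day 7), about 50 cases expected (11.4.4). 150 children per arm, with AAD 22% on control and 8% on BB-12 (11.2).

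**The plan's own figure.** 50 cases × 2 samples = 100 libraries. It reproduces exactly and leaves nothing for non-cases.

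**At the design rates**

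- Control cases: 150 × 0.22 = 33. BB-12 cases: 150 × 0.08 = 12. Total 45.
- Libraries: 45 × 2 = 90. The 10 left over would cover 5 children and are assigned to no one.
- Diarrhea-free children: 117 + 138 = 255, none sequenced under the rule.
- BB-12 expression comes from 12/150 = 8% of BB-12 children.
- If BB-12 prevents diarrhea and causes it in no child (an assumption), 33 − 12 = 21 of the 33 control cases (64%) would not have been cases on BB-12.

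**Budget limit.** 100/2 = 50 children, and 50/300 = 16.7% pooled AAD. Section 11.2 describes the primary outcome "with the rate of AAD in the general population estimated to be 20-35" percent. Its difference of 0.10 is taken here as 22% versus 12%.

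| AAD, control / BB-12 | Cases | Libraries needed | P(more than 50 cases), binomial |
|---|---|---|---|
| 22% / 8% | 45 | 90 | 0.18 |
| 22% / 12% | 51 | 102 | 0.52 |
| 20% / 20% | 60 | 120 | 0.92 |
| 22% / 22% | 66 | 132 | 0.99 |
| 35% / 35% | 105 | 210 | above 0.99 |

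**Detectable differences.** Two-sample t test, two-sided 0.05, 80% power, one feature, no multiplicity correction. The detectable difference is the d at which a noncentral t with n1 + n2 − 2 degrees of freedom and noncentrality d/√(1/n1 + 1/n2) gives 80% power.

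| Contrast | Group sizes | Detectable d (SD) |
|---|---|---|
| AAD vs non-AAD, as written | 45 vs 0 | none possible |
| AAD vs non-AAD, spare libraries used | 45 vs 5 | 1.35 |
| AAD vs non-AAD, stratified sample | 25 vs 25 | 0.81 |
| Arm contrast among cases, as written | 33 vs 12 | 0.97 |
| Weighted arm contrast, stratified sample | effective 18.4 vs 15.2 | 1.00 |

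The stratified sample takes 13 of 33 control AAD, 12 of 117 control non-AAD, 12 of 12 BB-12 AAD and 13 of 138 BB-12 non-AAD. The weights are 33/13 = 2.54, 117/12 = 9.75, 12/12 = 1.00 and 138/13 = 10.62. The Kish effective size is (Σw)²/Σw². For control this is 150²/(13 × 2.54² + 12 × 9.75²) = 18.4; for BB-12 it is 150²/(12 × 1.00² + 13 × 10.62²) = 15.2.

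**Size of the selection effect on the arm contrast.** Assume a normal liability to diarrhea, with arms differing only in the threshold. The mean liability of cases is φ(z)/p: 1.346 at 22% and 1.858 at 8%, a gap of 0.512. If the feature's correlation with liability is 0.1 to 0.5 (assumed; not in the documents), the spurious arm difference is 0.05 to 0.26 SD.

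**The case against.** The strongest reply is that section 11.4.5 lists anticipated results, not tests or estimands, and promises no randomized expression effect. Objective 3 also covers community structure, for which 16S profiling compares the arms in all 300 children. Case-only sequencing still gives expression with and without BB-12 in about 12 and 33 children, and the paired baseline-to-Day 7 change among cases is a sound use of the data. This stands, and it is why the matter is confined to the expression claims. It does not supply the missing non-AAD group.

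Three further points are fair:

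- **Cost to the paired analysis.** Cutting cases from 45 to 25 raises the detectable paired change from 0.43 to 0.58 SD of change. Among control cases, 33 to 13, it goes from 0.50 to 0.85 SD. Choosing depth in cases over a case/non-case contrast is legitimate, provided the stated aims follow.
- **Multiplicity.** The 0.81 SD is for a single feature. With Bonferroni over an assumed 100 to 1,000 features, 25 vs 25 detects about 1.3 to 1.5 SD.
- **Budget.** The count of 50 is a forecast and more than 50 cases has probability 0.18 at the design rates, so the overrun is a contingency. Still, a one-line selection rule would settle it.

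It can also be said that the footnote covers all cases without saying only cases, and that cases starting after Day 7 give a pre-diarrheal profile. But no library is allotted to a diarrhea-free child, and a later case is not a non-AAD control.

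**Conclusion.** The concern holds. Followed as written, the expression data can describe children with diarrhea. They cannot show what distinguishes AAD from non-AAD children, and they give no randomized estimate of the BB-12 effect on expression. The first conclusion rests on the text alone. The counts rest on the section 11.2 rates with 150 children followed per arm; with 10% loss (135 per arm) they become 40.5 cases and 81 libraries, which does not change the conclusion. The selection effect of 0.05 to 0.26 SD depends on an assumed correlation and is smaller than the imprecision of the arm contrast, so the missing comparison group is the main defect.

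The scope is a secondary, exploratory aim. Section 11.4.6 is affected only where clinical outcome means AAD yes or no. Within-case change, correlations with diarrhea duration or severity, resistance-gene expression, every 16S analysis, safety and the primary outcome stand. The plan should be corrected before sequencing starts.

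**What to change.** Before sequencing, make the rule and the claims agree in one of two ways.

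**(a) Keep the AAD/non-AAD expression question.** In section 11.4.4, replace the case-only rule with a random draw of about 50 children from the stored baseline and Day 7 samples, in arm-by-AAD strata with recorded sampling fractions. Take a whole stratum if it is smaller than its target. At the design rates this is the 13/12/12/13 split shown above. Compare AAD with non-AAD with arm in the model, and treat any sampling-weighted arm effect as exploratory. This needs no extra libraries or stool samples. It costs about 20 sequenced cases and the paired precision noted above, and it brings no gain for the arm effect. It creates an AAD contrast where there is none now.

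**(b) Keep case-only sequencing.** Limit section 11.4.5 to within-case description, remove the AAD/non-AAD expression claim, and label any arm difference as non-randomized. State that if more than 50 children have diarrhea, 50 are drawn at random within arm. This costs text edits only and gives up the AAD/non-AAD expression question.

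Under either option, give the metatranscriptome row of Table 8 its own footnote, because it now shares footnote 2 with the *C. difficile* row, whose rule should not change.
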